After Phase 2 starts, participants will be observed at the NIH for 2 days. They will then receive a phone call and/or email at approximately one and three weeks to monitor their status on the study drug or placebo by a health care professional. After the first month, the subjects will be monitored by phone and/or email monthly (month 2, 3, 4, and 5). Participants will be expected to take their dose three times per day for about six months. Adherence will be assessed by a pill count at their 3-month assessment and at their post-treatment visit (third visit). The pill count will be performed by the participant at home for the 3-month phone call assessment and by a member of our team at NIH during their third visit. Finally, the outcome measures will be obtained at the final visit 6 months (± 2 weeks) after start of treatment (about 12 months into the study). Six months after their third visit (± 2 weeks), the participant will be called for a post-treatment follow up. The participant (or parent) will be asked open-ended questions to assess their symptoms and current medication regime. They will also be asked to fill out the same fatigue and QoL scales completed during their visits, at home on CTSS. The participant will then be finished with the study. Please see Appendix A for a detailed Visits and Procedures Schedule.

b. Recruitment

Although RYR1 congenital myopathies constitute a rare disease, the PIs and AIs on this protocol work closely with patients with this condition and with patient groups such as the Muscular Dystrophy Association and Cure CMD. We will advertise the study through the patient groups by providing information about the study and posting it on their websites (Appendix B). We will

also provide a letter describing the study including contact information to health care providers in the neuromuscular field (Appendix D). If interested, potential participants can call the research coordinator listed on the advertisements.

Flyers have been created for healthy volunteer and patient populations (Appendix B). The patient flyer includes contact information for the Patient Recruitment and Public Liaison office (PRPL). We will distribute our flyers to the managers of the Facebook group pages entitled: “The RYR-1 Foundation”, which is found at this link:

<https://www.facebook.com/ryr1foundation/?fref=ts>, and

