If a patient reports Grade 3 side effects for diarrhea, nausea, vomiting, constipation, or abdominal pain, or any other Grade 3 side effect, according to the NCI Common Terminology Criteria for Adverse Events v.3.0, we will discontinue their participation. If Grade 1 side effects are reported, we will monitor them by phone and/or email and keep them on the drug. If Grade 2 side effects are reported, we will discontinue drug until the side effect resolves and then resume administration with careful observation for reoccurrence. Monitoring for grades 1 and 2 side effects will include weekly phone calls and/or emails until symptoms subside. If symptoms worsen subjects will visit their primary care physician. Subjects who experience grade 3 symptoms will receive an assessment by our healthcare provider and will be advised to schedule a prompt appointment with their local healthcare provider. We will also encourage them to contact us at any time with questions or concerns.

We will offer an evaluation at NIH for any participant who would like to return for an evaluation of side effects, such as, but not limited to, local participants. This evaluation will include a history and physical examination, discussion with the medical advisory investigator,

and appropriate consults, for example a GI consult.

An informational letter (Appendix F) to the participant's physician will be given to each subject to give to their primary care provider.

8. Subject Safety Monitoring

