Investigators will evaluate participants for any foreseeable safety concerns before study procedures are performed. Investigators will allow participants to miss individual procedures (other than the two primary outcome measures— urine collection for 15 F2t-isoprostane levels and 6MWT), at one or all study visits, if safety concerns arise. Examples include: If a participant has a recent history of knee dislocation or knee injury, that participant will be excluded from the Biodex procedure. If a participant has an increased risk of blood clotting, that participant will not perform the arterial occlusion test. If a participant is at NIH and recently recovered from a rhabdomyolysis crisis, that participant will not perform CPET at that visit, but may perform CPET at following visits, if deemed safe at that time. If a participant has certain types of metal in their body, that participant will not perform the MRI procedure at any visit. Investigators will ask participants about potential safety concerns for each procedure and participants are also asked to inform study investigators about potential risk factors in the consent. Investigators will have a participant miss certain non-primary outcome measure procedures, due to safety concerns, at their discretion. Participants will remain enrolled in the study if they are able to safely perform the two primary outcome measures and are also able to safely consume the study medication/placebo, given the expected side effects. [name] can withdraw a participant, at any time, if she believes continuation is not in their best medical interest, or if the participant is unable to comply with the study.

For monitoring for NAC administration, please see previous section under “Steps Taken to Minimize Risk”.

For other individual monitoring plans, please see previous section under “Steps Taken to Minimize Risk.”

Criteria for stopping procedures in an individual include:

If a patient reports Grade 3 side effects for diarrhea, nausea, vomiting, constipation, or abdominal pain, or any other Grade 3 side effect, according to the NCI Common Terminology

Criteria for Adverse Events v.3.0, we will discontinue their participation.

Criteria for individual subject withdrawal from the study

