The primary analysis will be an intent-to-treat (ITT) analysis, i.e. all randomized participants will be included in the analysis. The mechanism for missing data will be evaluated. If missing data are unrelated to the intervention or primary outcome (i.e. missing completely at random or missing at random), the analysis will be based on multiple imputations (20-40 imputed datasets, depending on the extent of the missing data) with a pooled average of the 20-40 imputations included in the final dataset and used in hypothesis-testing analyses. Minimum and maximum value constraints for imputed data will be determined using *per protocol* averages.

Because of uncertainties regarding the true effect size of NAC treatment in our patient population, and the rare nature of this disease possibly limiting accrual, we plan to perform a sample size reevaluation and interim analysis once 30 patients have completed the trial, i.e., when 40% of our potentially achievable accrual reach Month 12.

For the sample size reevaluation, and based on the observed data so far, we will calculate the following: the control group delta and its standard deviation and the standard deviation of the delta for the active arm. Based on these observed parameter values for urine 15-F2t-isoprostane, we will re-calculate the sample size and compare it to the current N=76.

Based on O'Brien-Fleming boundary calculations (O'Brien and Fleming, 1979), the interim analysis will result in one of 3 actions:

1. If there is strong indication of no benefit of NAC in decreasing 15 F2t-isoprostane levels, i.e. if the observed standardized treatment effect is less than -3.36, we will consider stopping the study early for futility.
2. If there is no clear indication of benefit of NAC decreasing 15 F2t-isoprostane levels, i.e. if the observed standardized effect size is between -3.36 and 3.36, we will continue the study and analyze the data at the completion of the study.
3. If there is strong indication that the NAC treatment decreases 15 F2t-isoprostane levels, i.e. if the observed standardized treatment effect is greater than 3.36, we will consider stopping the study early for efficacy.

Stopping the trial early when there is strong evidence for futility or efficacy will reduce patient burden, decrease excess costs, and provide a potential treatment sooner for this rare disease, which currently has no treatment.

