There will be no difference in mean corrected 15-F2t-isoprostane concentration or 6MWT distance, between the *RYR1*-RM and otherwise healthy individuals.

Alternative Hypothesis (H_1)

Corrected 15-F2t-isoprostane concentration will be significantly increased and 6MWT total distance will be significantly decreased in *RYR1*-RM myopathy patients when compared to otherwise healthy individuals.

2. After 30 participants complete their 2nd visit at 6 months (prior to starting study drug/placebo), disease progression will be assessed using paired t-tests to determine changes between 0 and 6-month visits for each outcome measure. For the primary outcome measures (corrected 15-F2t-isoprostane concentration and 6MWT) change between 0 and 6-month time points will be assessed. This analysis will be repeated when all 6-month visits are completed.

Null Hypothesis (H₀)

Corrected 15-F2t-isoprostane concentration and 6MWT total distance will not change significantly between 0 and 6 months in *RYR1*-RM myopathy patients.

Alternative Hypothesis (H₁)

There will be a statistically significant difference between 0 and 6-month values for corrected 15-F2t-isoprostane concentration and/or 6MWT total distance in *RYR1*-RM myopathy patients.

Intervention phase analyses (month 6 to month 12)

- Use an independent t-test (or non-parametric equivalent) to compare pre-intervention (month 6) values for demographics, urine isoprostane and six-minute walk test between NAC versus placebo groups.
- Using multiple imputation (x40 datasets and minimum/maximum value constraints from *per protocol* data) impute missing month 12 data.
- The following GLM should be run both *per protocol* and with ITT datasets.
 1. Run a general linear model comparing month 12 month corrected 15-F2t-isoprostane concentration (corrected_f2-isop_month12, corrected_f2-isop_PGF2alpha_ratio_month12) between NAC and placebo groups controlling for pre-intervention value. Run this model again controlling for established *a priori* confounders including age, sex, height, weight, BMI, smoking status, alcohol status. Variables that do not contribute significantly to the model may be removed. (Exclude RYR023, RYR024, and all healthy volunteers).

Null Hypothesis (H₀)

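### The Grade 3 rule ends participation rather than only study drug, so month-12 primary outcomes are likely to be missing for a treatment-related reason, and no analysis tests how they are imputed (minor)

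*Protocol*

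**What the plan says.** Protocol section 7 grades the response to side effects. Grade 1 is monitored on drug. Grade 2 interrupts the drug until resolution. For Grade 3 the sentence opens "If a patient reports Grade 3 side effects for diarrhea, nausea, vomiting, constipation, or abdominal pain" and continues "any other Grade 3 side effect, according to the NCI Common Terminology Criteria for Adverse Events v.3.0, we will discontinue their participation". Section 8 repeats it under the criteria for stopping procedures in an individual. Section 8 also makes staying enrolled depend on being able to take the study medication or placebo safely.

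Section 7 offers an optional return to NIH for side effects: "This evaluation will include a history and physical examination, discussion with the medical advisory investigator", plus consults. It does not mention the urine sample or the walk test. Section 4a places the primary assessment later: "the outcome measures will be obtained at the final visit 6 months" after treatment starts.

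On analysis, Protocol section 10b states: "The primary analysis will be an intent-to-treat (ITT) analysis, i.e. all randomized participants will be included in the analysis". It then says "The mechanism for missing data will be evaluated" and makes multiple imputation conditional: "If missing data are unrelated to the intervention or primary outcome", which it equates with missing completely at random or missing at random. No method is given for the other case.

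The SAP (Intervention phase analyses) has one instruction: "Using multiple imputation (x40 datasets and minimum/maximum value constraints from" the per-protocol data, applied to missing month-12 values. The Protocol's condition is not repeated and no imputation predictors are named. The linear models are run on both the per-protocol and the ITT datasets.

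**The concern.** An ITT comparison at month 12 includes patients who stopped NAC, with whatever outcome they have off drug. The Grade 3 rule probably prevents that outcome from being measured. Every NAC value available to the imputation then comes from patients who were not withdrawn under this rule. If the benefit fades after stopping, a model that includes arm gives withdrawn NAC patients on-drug values and makes the effect look larger than it is among all randomized patients.

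Withdrawal for a drug side effect is also the plainest example of missingness related to the intervention, which is the case the Protocol leaves without a method and the SAP imputes anyway. The rule sits badly with section 8, which lets patients miss any procedure for safety reasons except the two primary outcomes.

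**Working it through.** **Inputs.**
- 50 patients per arm: accrual ceiling on the Protocol's opening pages.
- 76 completers out of 100: section 3a and the same ceiling, so 24 planned losses, 24/100 = 24%. Section 10b attaches per-group wording to 76 and 24, but the share is still 24/(76 + 24) = 24%.
- Randomization at the end of the month-6 visit: section 4a.
- Number of NAC patients withdrawn at Grade 3 (k): not stated. Assumed 0, 1, 2 or 4.
- Assumed: on-drug effect d = 0.5 SD, baseline correlation 0.5, effect fully lost after stopping.

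**The plan's own figure.** With a difference of 1.7, SDs of 2.34 and 2.80 and two-sided alpha 0.05, the Satterthwaite t-test has power 0.798 at 37 per group and 0.809 at 38. The stated 38 per group reproduces, and 76/(1 − 0.24) = 100 gives the ceiling. The point here disputes none of these figures.

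**Plausible k.** Section 7 cites 18 patients at about this dose, 7 with mild symptoms and none needing clinical monitoring. With 0 of 18, the exact one-sided 95% upper limit is 1 − 0.05^(1/18) = 15.3%. So 4 of 50 (8%) is not excluded, though not expected.

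**Step 1: the Grade 3 rule, arm in the imputation model.** Withdrawn NAC patients are imputed around the on-drug mean, so the estimate is d. The true ITT effect is d(1 − k/50). The overstatement is d × k/50, and the standard error is sqrt(0.75 × 2/50) = 0.173 SD.

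| k | share of d | SD units | in SEs |
|---|---|---|---|
| 0 | 0% | 0 | 0 |
| 1 | 2% | 0.01 | 0.06 |
| 2 | 4% | 0.02 | 0.12 |
| 4 | 8% | 0.04 | 0.23 |

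A simulation (50 per arm, only the withdrawn patients missing) gave +1.9%, +4.1% and +8.0% for k = 1, 2, 4. Reference-based imputation of the same patients gave 0.0%, 0.0% and +0.1%. Clipping imputed values to the observed minimum and maximum gave +1.9%, +3.9% and +7.7%, so the SAP's value limits are not the cause. The bias is proportional to d, so it is zero if NAC has no effect, and it is less if part of the effect persists.

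**Step 2: a separate matter, arm left out of the imputation model.** With a share m missing in each arm, imputed values in both arms centre on the pooled mean, d/2 above placebo. The NAC mean is (1 − m)d + m·d/2 and the placebo mean is m·d/2, so the estimate is (1 − m)d.
- All 24 planned losses after randomization: m = 12/50 = 24%, estimate 0.76d.
- Half of them before randomization (assumed): 100 − 12 = 88 randomized, 44 per arm, m = 6/44 = 13.6%, estimate 0.86d.

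The gap from the true ITT effect at m = 24% is 0.76 − (1 − k/50): −24, −22, −20 and −16 points for k = 0, 1, 2, 4. It is largest when nobody is withdrawn at Grade 3. In simulation at 24% missing in each arm of 50 (effect 0.57 SD), power was 0.78 with arm in the model and 0.58 without.

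**The case against.** Five points can be made in the plan's favour.

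- **Month-12 loss is inferred.** No sentence cancels the visit, and Appendix A, the visit schedule, is not in the available text. A reader might take the loss as certain; the documents support only that it is likely. The wording that ends participation, the heading it sits under in section 8 and the enrolment condition point that way, and nothing points against it.
- **The SAP does run a second analysis.** It would be wrong to say there is no sensitivity analysis, because the models are also fitted per protocol. That set would be expected to leave out these same patients, so it does not test how they are imputed. The gap is specific to the missing-data assumption.
- **The 24% attenuation is not a cost of the Grade 3 rule.** A reader might join the two. Step 2 shows the gap shrinking as k rises. It also requires arm to be omitted, and silence about predictors is not evidence of that. And 24% is an upper bound: planned losses also cover the six months before randomization, and patients lost then are outside the ITT set.
- **Some of this is already covered.** The Protocol promises to evaluate the mechanism, and the SAP tabulates adverse events by arm, with severity and causality for NAC. That stands, but neither supplies a fallback or links events to missing month-12 data.
- **The consequence is small.** At 0.06 to 0.23 SE the bias would rarely change a conclusion, and it cannot create an effect where none exists. This also stands, and it sets the severity.

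**Conclusion.** The point holds, at minor severity. The Grade 3 rule as written is likely to remove primary outcomes for a treatment-related reason under an ITT analysis. The SAP imputes them without the Protocol's condition, and no planned analysis tests that step.

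The size attributable to the rule is an overstatement of about 2% to 8% of the on-drug effect for one to four NAC withdrawals. This rests on 50 per arm, full loss of effect after stopping and arm in the imputation model. Fewer randomized patients would raise the percentage for the same k; at 44 per arm, 1/44 to 4/44 is 2.3% to 9.1%. The actual k is not given and may be zero.

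The possible attenuation from leaving arm out (at most about 24%, about 14% if half the planned losses precede randomization) is a separate specification gap affecting all missing month-12 data.

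**What to change.** **(a) For any remaining visits or reuse of the design.** Reword the Grade 3 rule in sections 7 and 8 so that it stops study drug. Keep the safety trigger unchanged, and still ask these patients for the planned month-12 urine sample and, if safe, the six-minute walk. The measures are already scheduled. The downside is that some patients will decline off-drug follow-up. The study is closed to data analysis, so visits already lost cannot be recovered.

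**(b) In the SAP.** State that treatment arm and pre-intervention value are in the main imputation model. If any NAC patient who stopped drug lacks month-12 data, add one reference-based (placebo-arm) or delta-adjusted imputation as a sensitivity analysis for both primary outcomes. Label it post hoc if it is added after unblinding. The cost is a sentence and one extra imputation run on locked data; if no NAC patient meets the condition, the extra run is not needed.

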- Patients who have a severe pulmonary dysfunction (FEV1 < 40% predicted) or evidence of pulmonary exacerbation. Pulmonary exacerbations refer to an acute worsening of respiratory symptoms that result from a decline in lung function (Flume et al., 2009). Participants may present with increased coughing, increased dyspnea, increased haemoptysis, increased fatigue, decreased pulmonary function by a min of 10%, or a change in sputum color (Bilton et al., 2011).
- Pregnant and breastfeeding women.
- Consumption of antioxidants [including NAC, GSH, melatonin, Immunocal (Immunotac

Research, Vandreuil-Dorion, QC, Canada), Nacystelyn (Galephar, Brussels)] in the 4 weeks before recruitment.

- Daily use of acetaminophen (including Percocet, Vicodin, Oxycodone, Excedrin, and other acetaminophen-containing drugs), nitroglycerine, or carbamazepine during the past 7 days.
- Current use of Angiotensin-converting enzyme (ACE) inhibitors or Angiotensin Receptor Blockers (ARBs)
- Patients who have ever used Beta2-adrenergic agonist tablets, for the purpose of increasing muscle mass (such as albuterol tablets).
- For the muscle biopsy procedure only (second and third visits, if applicable): Patients who have taken Aspirin, Ibuprofen, Advil, Motrin, or Aleve within the 3 days prior to the muscle biopsy procedure, and/or patients who have taken Plavix, fresh garlic, ginkgo, or ginseng 5 days prior to the muscle biopsy.
- Participation in trials for other therapeutic investigational drugs simultaneously or 4 weeks before recruitment.

Other clinically significant medical disease that, in the judgment of the investigators, would expose the patient to undue risk of harm or prevent the patient from completing the study. Examples include anemia (defined as Hgb < 8 gm/dl), an inability to walk safely without assistance for at least 6 minutes, and/or an inability to consume at least 6 ounces of fluid, 3 times a day, either orally or via G-tube. Patients with comorbidities (i.e. cancer, epilepsy) will be carefully assessed to determine if their comorbidity could lead to confounding or safety issues, should their participation continue.

Healthy Volunteers:

- Diagnosis of RYR1-related myopathy or other neurological disorder (by neurological exam, genetic testing, or muscle biopsy)
- Complaints of fatigue or weakness
- Consumption of antioxidants [including NAC, GSH, melatonin, Immunocal (Immunotac

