Motor Function Measure 32 (MFM): The MFM is a generic scale which provides a measurement of the effects of muscle weakness in neuromuscular diseases (NMD). Assessments are based on posture and movements of the whole body. It is applicable to both ambulant and non-ambulant patients with a wide range of disease severity. The patient is asked to roll, sit, lift head from prone and supine position, get up from a lying position, prop on arms, kneel, crawl, stand and step. This test will be combined with timed tests (floor to stand, ascend/descend 4 steps). Time to complete both tests: approximately 60 minutes.

6 Minute Walk (6MWT): The self-paced 6MWT assesses the submaximal level of functional capacity. The patient is asked to walk for 6 minutes with their best effort. A clinician accompanies the patient during the test to ensure patient's safety. Heart rate and blood pressure is monitored before and after exercise and after 5 minutes of recovery to ensure safety of the patient. The patient is allowed to stop if he feels tired. Time to complete the entire test: approximately 20 minutes.

Biodex: Biodex will be used to test muscle groups using a dynamic sub-max fatigue test with a repetitive motion. Blood pressure will be taken prior to testing to confirm the patient is not hypertensive (>140/90). Clinicians will assess participants for previous knee injury prior to testing. The biodex test will not be performed if the participant has a history of knee injury. Clinicians will provide a 5-minute break immediately after the test, during which time the patient may not rise from the seat. Time to complete the entire test: approximately 60 minutes.

Phlebotomy, Genetic Testing, and Exome Sequencing: Phlebotomy will be performed to obtain blood for liver function testing at baseline and glutathione levels. Blood and blood products may be analyzed or stored for creatine kinase (CK) level, lactate/pyruvate ratio, cell counts, blood chemistries, molecular genetic analysis and DNA banking. The lab will draw blood for DNA to confirm a genetic mutation, for exome sequencing, and/or for future studies and other clinical lab testing. If confirmatory genetic testing of an enrolled family member reveals that a participant does not have an *RYR1* mutation causative of RYR1-RM, the participant will be informed and withdrawn from the study.

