CPET: VO₂ peak, peak power, test duration of entire test, time to AT, work efficiency (VO₂ work rate slope), and ventilator equivalent (VE/VO₂) will be obtained.

EIM: An EIM will be used to measure skeletal muscle health. Resistance, reactance and phase of multiple muscles will be measured.

6MWT: Meters walked in 6 minutes will be recorded (to the nearest meter). Distance in meters will be recorded at each minute interval. Speed will be calculated.

Timed tests: Participants will be timed in the performance of the following: 10 meter walk test, supine to stand, ascend 4 stairs, descend 4 stairs. They will be graded on an ordinal scale.

Myotools: Force required for participants to squeeze the grip dynamometer and pinch the pinch gauge. The best effort of 3 trials will be recorded for grip and pinch strength.

Biodex: Biodex will be used to test muscle groups using a dynamic sub-max fatigue test with a repetitive motion. Blood pressure will be taken prior to testing to confirm the patient is not hypertensive (>140/90). Outcome measures will include peak torque measured in newton meters and number of repetitions to 50% decline in peak torque.

Arterial Occlusion Muscle Oxygenation Capacity Test: The tissue saturation index will be calculated as $TOI = [O_2-Hb] / Tot-Hb$. The rate of decline and rise in TOI will be the main muscle tissue saturation measures.

MFM: The final outcome is a percentage based score of each domain and the total score.

PROMIS, FACIT, MFI, NeuroQoL: Questionnaires will be scored based on each scale's requirements.

MRI: The outcomes will be muscle mass via T1, fat composition via T1 to T2 comparison, water composition via T1 to T2 comparison and chemical composition (lipids) via MRS.

Saliva collection: FBI, melatonin, cortisol and DHEA levels will be obtained.

Qualitative interview: Responses to the interview will be obtained and major themes will be identified.

10. Statistical Analysis

a. Analysis of data/ study outcomes

Natural history study (Phase 1 of protocol):

During the natural history phase of the study, we will take one look at the data prior to the final analysis with the following two approaches:

- 1) After 30 participants complete their baseline visit, we will compare their baseline outcome measure values against healthy controls. For the primary outcomes, 15-F2t-isoprostane and 6MWT distance will be compared against healthy individuals. This analysis will be repeated when all baseline visits are completed.

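### Inability to perform the six-minute walk has no score, may end follow-up, and under the SAP would be filled in with a distance from the range of patients who could walk

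*Protocol*

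**What the plan says.** **Enrolment and follow-up (Protocol Section 8).** Procedures may be skipped for safety reasons, with two exceptions: "Investigators will allow participants to miss individual procedures (other than the two primary outcome measures", that is, urine collection for isoprostane and the 6MWT. The section then says "Participants will remain enrolled in the study if they are able to safely perform the two primary outcome measures", and adds that they must also be able to take study medication safely. A participant can be withdrawn on medical grounds "or if the participant is unable to comply with the study".

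**Walking ability at entry (Section 3c).** Among the examples of excluding conditions is "an inability to walk safely without assistance for at least 6 minutes". Inability seen after randomisation is therefore normally an on-study event.

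**Conduct and scoring (Sections 4d and 9).** "The patient is allowed to stop if he feels tired", and "Meters walked in 6 minutes will be recorded (to the nearest meter"). Neither document gives a score for a patient who cannot attempt the walk.

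**Missing data (Section 10b).** Under intention to treat, "all randomized participants will be included in the analysis". The mechanism of missingness is to be assessed, and multiple imputation applies if data are missing completely at random or at random (MCAR/MAR). No method is named for any other case. "Minimum and maximum value constraints for imputed data will be determined using" per-protocol averages.

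**SAP, Intervention phase analyses.** Missing month 12 data are imputed in 40 datasets, with a minimum and maximum taken from per-protocol data. The MCAR/MAR condition does not appear. The 6MWT model compares month 12 distance between arms, adjusted for the baseline value, in both the intention-to-treat and per-protocol datasets. No analysis for data missing not at random is planned.

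**The concern.** A distance that is missing because the patient can no longer walk is missing because of its own value. MAR then fails, and the most adverse result on a primary outcome leaves the data. If the SAP is followed as written, the gap is filled with a plausible walking distance. An imbalance between arms in loss of walking would then be largely absent from both planned 6MWT analyses: the intention-to-treat one because the value is imputed, the per-protocol one because there is no value.

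There is a second, indirect cost. Urine isoprostane needs no walking, and it is the outcome on which trial success is defined (Section 10a). If inability to walk leads to withdrawal, that sample can be lost for an unrelated reason, because no collection after withdrawal is described and withdrawn patients are not replaced (Section 3a).

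**Working it through.** **1. The plan's own figure.** Section 10b gives 38 per group for a glutathione change of 1.7 versus 0, SDs 2.34 and 2.80, two-sided alpha 0.05 and 80% power (Satterthwaite t-test).

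- Standard error at n = 38: √((2.34² + 2.80²)/38) = √(13.3156/38) = 0.592. Noncentrality: 1.7/0.592 = 2.87.
- Power is 79.8% at n = 37 and 80.9% at n = 38. The figure of 38 reproduces.
- It agrees with the 76 completers in Section 3a. Section 10b also gives 76 per group and a ceiling of 200, which conflicts with Section 3a and with the 100 patients (50 per arm) on the cover pages. I use 38, and 50 as the alternative.

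**2. The path of a patient who cannot walk at month 12.**

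| Step | Protocol | SAP |
|---|---|---|
| Stay in follow-up? | Tied to performing the walk; withdrawal discretionary | Not addressed |
| Score for inability | None | None |
| May the value be imputed? | Only if MCAR/MAR, which fails here; no fallback | Yes, no condition |
| Limits on imputed value | Per-protocol averages | Per-protocol data |

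Under the SAP the imputed distance cannot fall below the shortest per-protocol distance.

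**3. Size, simple arithmetic.** The documents give no 6MWT mean, SD or rate of lost walking, so the inputs are assumptions: k = 1 to 3 non-walkers in one arm, each given m = 200 to 400 m instead of 0 m. Shift in that arm's mean = k × m / n.

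- n = 38: 1 × 200/38 = 5.3 m, up to 3 × 400/38 = 31.6 m.
- n = 50: 1 × 200/50 = 4 m, up to 3 × 400/50 = 24 m.

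This becomes a shift in the arm difference only if the losses are in excess in one arm.

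**4. Size, simulation.** Assumptions: 38 per arm, no drug effect, mean 300 to 500 m, SD 100 m, correlation 0.9 with baseline, lowest-baseline patients lose walking, baseline-adjusted model. Imputed values were clipped to the completers' range.

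| Excess non-walkers in one arm | Shift in arm difference, 0 m scoring versus bounded imputation |
|---|---|
| 1 | about 3 to 8 m |
| 2 | about 7 to 18 m |
| 3 | about 12 to 28 m |
| 2 in each arm | about 0 m |

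The bounded-imputation estimate stayed within about 1.5 m of zero throughout. With one non-walker and a mean of 300 m, the floor averaged 72 m and the imputed value 123 m. The imputed values thus lie well above the floor, so the MAR model itself does most of the work. Lifting the bounds alone would not restore the lost outcome.

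For scale, 38 per arm gives 80% power for (1.960 + 0.842) × √(2/38) = 0.64 SD, or about 64 m at the assumed SD of 100 m.

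**5. Urine.** On the glutathione inputs, losing 1, 2 or 3 patients per arm from 38 lowers power from 80.9% to 79.8%, 78.7% or 77.5%. This is only a guide, since those are not isoprostane data.

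**The case against.** A reader might infer that patients who lose walking ability are removed, imputed as walkers, and lose their urine data as a matter of rule. The documents do not support that.

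- **Withdrawal is not stated.** Section 8 says 'if', not 'only if', and the power to withdraw is discretionary. The specific withdrawal grounds elsewhere (Grade 3 side effects, missed doses, no causative mutation, liver findings) do not include loss of walking.
- **The Protocol has a guard.** Its MCAR/MAR condition would keep these values out of the imputation. Unconditional imputation comes from the SAP alone.
- **Partial decline is not hidden.** Early stopping is allowed and the metres walked count. Such short walks may also lower the imputation floor. Only complete or unsafe inability is at issue.
- **Urine loss is inferred from silence.** Urine is due at each visit and is itself one of the two procedures that may not be missed. Nothing ends its collection because a walk was not done.
- **Cases may be few.** Section 1 describes the disease as not degenerative, with motor scores stable over one year, and treatment lasts six months. The accrual of 100 against 76 completers already allows for 24 losses.
- **Scoring 0 m or worst rank is a choice of estimand**, not the correction of an error.

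All of this stands as a limit on certainty and size. It does not remove the gap: the Protocol has no method once MAR fails, the SAP omits the condition, and no planned analysis reflects inability to walk.

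**Conclusion.** The point holds in a limited form. Follow-up is linked to performing a primary outcome, inability to perform it has no score, and the SAP's unconditional, bounded imputation would replace it with a walker's distance. The 6MWT comparison can be biased if such losses differ between arms.

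The size is unknown and probably small. The 5 to 32 m shift (4 to 24 m at 50 per arm) concerns one arm's mean and rests on an assumed 1 to 3 excess cases and an assumed 200 to 400 m. Equal losses move the arm difference by about 0 m. The definition of trial success does not depend on the 6MWT. For isoprostane, the documents support only that collection after withdrawal is not provided for; they do not show that any sample was lost. A count of missing month 12 walks by arm and reason would show whether the issue arose at all.

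**What to change.** The study is being closed to data analysis (Protocol Section 10b) and the SAP works from locked files, so only the analysis part can still change here.

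**In the SAP, now:**
1. Restore the Protocol's MCAR/MAR condition for imputation, and reconcile the bounds: averages in the Protocol, data in the SAP.
2. Do not apply per-protocol bounds to a 6MWT that is missing because of disease-related inability.
3. Report missing month 12 6MWT by arm and reason. If no patient was unable to walk, one sentence closes the matter.
4. Add one sensitivity analysis that gives disease-related inability the worst rank or 0 m, labelled as added after data lock. This step is needed as well as step 2, because unbounded imputation under MAR would still give walking distances.

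**For future protocol wording:** separate inability to perform the 6MWT from leaving outcome follow-up, so that month 12 urine is still collected. The safety judgement about whether a patient should attempt the walk is unchanged.

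Cost: changes to SAP wording, one small table and one extra sensitivity analysis.
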